## 4 STUDY DESIGN

### 4.1 OVERALL DESIGN

SYNIVUS-DAPT is a prospective multicenter single-arm pilot study designed to characterize the safety of 1 month of dual antiplatelet therapy (DAPT) in a high bleeding risk (HBR) patient population who are undergoing iLab™ IVUS-guided percutaneous coronary intervention (PCI) with a SYNERGY™ Stent System.

Hypothesis – one (1) to thirteen (13) month rates of cardiac death or myocardial infarction (SCAI definition), and Stent thrombosis after Boston Scientific IVUS-guided SYNERGY™ Stents implantation will be low and provide key hypothesis-generating information to inform future larger scale clinical studies.

Patients will be screened as per standard of care (please see Section 1.3 Schedule of Activities). Eligible patients will undergo iLab™ IVUS-guided PCI with SYNERGY™ Stent System on Day 1 followed by safety laboratories (CBC w Diff, Platelets, Basic Metabolic Panel, PT/INR, CPK/CK-MB or troponin) and EKG within 24 hours of procedure completion. At 30 days ( $\pm$  7 days) patient will return to clinic for evaluation, followed by phone follow up at 30 days post DAPT cessation (60 days post PCI) 6 months ( $\pm$  14 Days) and at 12 months ( $\pm$  30 days) post-DAPT cessation (7 and 13 months post-procedure) for evaluation of adverse events and endpoints.

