## 1.2 STUDY DESIGN

## 1.3 SCHEDULE OF ACTIVITIES (SOA)

Procedures	Screening/ Baseline a	Index Procedure (Day 1)	Post-Index Procedure b (Prior to discharge)	30 Days (+ 7 days) Post PCI ) (in office)	60 days (+7 days) Post PCI (In office or via phone)	7 months (+14 days i ) Post PCI (In office or via phone)	13 Months (+ 30 days j ) Post PCI (In office or via phone)
Informed Consent	X						
H&P c	X						
CBC w Diff, platelets	X		X				
BMP	X		X				
PT/INR (only if on warfarin, liver disease or severe anemia)	X		X				
CPK, CK-MB or Troponin-I	X		X d				
EKG	X		X				
ConMeds (Only Cardiac)	X		X	X	X	X	X
Cardiac Cath w PCI		X					
ASA LD	X e						
ASA MD		X f		X		X	X
P2Y12 LD		X g					
P2Y12 MD			X h	X		X	X
AE assessment		X	X	X	X	X	X
Angina assessment k				X	X	X	X
Angina Questionnaire				X			
EDC Completion	X	X	X	X	X	X	X

- a to be completed  $\leq$  7 days prior to Index procedure
- b To be completed within 24 hours after Index procedure
- c Determination of high risk of bleeding (HRB)
- d Perform 2, 6-8 hours apart, if cardiac enzyme levels are elevated (i.e. exceed the upper limits of normal as defined by local guidelines), serial measurements be performed until a decline is noted. If same day discharge draw one set immediately post PCI then 2nd set @ 6-8 hours after
- e Aspirin loading dose (LD) = 325 mg. Start day of procedure (if not on chronic ASA)
- f Aspirin maintenance dose (MD) = 81 mg. Start the day after aspirin loading dose
- g P2Y12 Inhibitor Loading Dose (investigator preference): clopidogrel 600 mg PO x 1 or 75 mg PO daily x 4; prasugrel 60 mg PO x 1; ticagrelor 180 mg PO x 1. Start within 7 days of procedure.
- h P2Y12 Inhibitor Maintenance Dose (investigator preference): clopidogrel 75 mg PO daily; prasugrel 10 mg PO daily; ticagrelor 90 mg PO BID. Start day after P2Y12 inhibitor loading dose
- i 6 months post DAPT cessation
- j 12 months post DAPT cessation
- k Angina Assessment only at 60 days, 7 months and 13 months

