**1. 30 Day Post PCI Visit (+ 7 days) in person Visit:****Requirements:**

- Angina Assessment including completion of the angina assessment questionnaire
  - Evaluate for cardiac events: recurring angina, unstable angina, revascularization (TLR or other) or another condition in the opinion of the investigator would prevent stopping DAPT
- Assessment of adherence to DAPT: Interruptions, missed doses, changes in DAPT Medication
- Adverse event assessment and reporting
- Cardiac con medications (including Aspirin)
- DAPT cessation

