#### 6.4 STUDY INTERVENTION COMPLIANCE

Compliance to DAPT regimen will be ascertained at the 1-month follow-up visit and will be used to determine if the subject is eligible for discontinuation of P2Y12 inhibitor. During the 1-month follow-up visit, the subject will also be asked about any significant interruptions (greater than 3 days) in the prescribed index procedure.

Follow up at 30 days post DAPT cessation either by phone or clinic visit to assess angina status and targeted endpoints.

Note: All enrolled subjects who receive a SYNERGY™ Stents must be followed at all milestones through 13-months, regardless of eligibility to discontinue DAPT.

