### 7 STUDY INTERVENTION DISCONTINUATION AND PARTICIPANT DISCONTINUATION/WITHDRAWAL

#### 7.1 DISCONTINUATION OF STUDY PARTICIPATION

Subjects should not discontinue P2Y12 inhibitor (the patient will remain in the study until 13 months unless consent to participate is withdrawn) at 1 month if any of the following criteria are met:

- Subject experiences a stroke, MI, PCI, CABG and/or stent thrombosis, during the 1 month period following the index procedure
- Subject is non-compliant with DAPT regimen during the 1 month period following the index procedure. Non-compliant is defined as: DAPT interruption for at least 3 days.
- Subject judged to have another condition rendering them inappropriate for discontinuation from P2Y12 inhibitor at 1 month.

An investigator may discontinue or withdraw a participant from the study if:

- Pregnancy occurs
- Significant study non-compliance beyond DAPT compliance issues

- Continued participation in the study would not be in the best interest of the participant due to other conditions
- The participant is unwilling or unable to discontinue DAPT within 7 days after 30-day post-procedure visit
- Other unforeseen reason

Additionally, participants may withdraw from participation in the study at any time upon their own discretion and a request to the site.

The reason for participant discontinuation or withdrawal from the study will be recorded on Case Report Form (CRF). Subjects who sign the informed consent form but screen fail due to inclusion or exclusion criteria requirements will be replaced.

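### Section 4.1 gives two-sided visit windows where 1.3 and 6.1.1 give plus-only ones, so the visit that judges eligibility to stop the P2Y12 inhibitor may fall at day 23 and the final contact about 30 days before month 13.

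*Combined protocol and SAP*

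**What the plan says.** Section 4.1 sets the eligibility visit at 30 days with a ± sign before its window, and from that sign the text reads "7 days) patient will return to clinic for evaluation, followed by phone follow up at 30 days post DAPT cessation". The same sentence puts ±14 days on the contact 6 months after DAPT cessation and ±30 days on the one 12 months after it (7 and 13 months after the procedure).

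The Schedule of Activities in 1.3 has "30 Days (+ 7 days) Post PCI", +14 days at 7 months, and "13 Months (+ 30 days" for the last contact. Section 6.1.1 has "30 Day Post PCI Visit (+ 7 days) in person Visit" and prints no window for the later contacts.

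The 30-day visit is more than a routine check:
- Section 6.4 says that DAPT compliance "will be ascertained at the 1-month follow-up visit and will be used to determine if the subject is eligible for discontinuation of P2Y12 inhibitor".
- Section 6.1.1 lists DAPT cessation among the requirements of the visit.
- Section 7.1 bars cessation if "Subject experiences a stroke, MI, PCI, CABG and/or stent thrombosis, during the 1 month period following the index procedure". It also bars cessation after a DAPT interruption of at least 3 days in the same period.

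The primary endpoint (Sections 1.1 and 3) runs from 1 to 13 months in the as-treated population, defined as those eligible for cessation at 30 days.

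**The concern.** Two sets of windows stand in the current text, and no sentence says which governs. A visit on day 25 complies with 4.1 but is outside the window in 1.3 and 6.1.1.

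The early side of the 4.1 window matters at two contacts. At the 30-day visit, the investigator would judge a one-month period that has not ended, and that judgement decides who stops the P2Y12 inhibitor and who enters the primary analysis population. At the last contact, follow-up could end about a month before the endpoint window closes. What is at stake is the safety of the cessation decision in individual patients and, to a lesser degree, complete ascertainment of the primary endpoint.

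**Working it through.** **Windows side by side** (days after PCI; a month taken as 30.4375 days, an assumption)

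| Contact | Section 4.1 | Section 1.3 | Section 6.1.1 |
|---|---|---|---|
| 30 days | 23 to 37 | 30 to 37 | 30 to 37 |
| 7 months | about 199 to 227 | about 213 to 227 | none printed |
| 13 months | about 366 to 426 | about 396 to 426 | none printed |

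**Eligibility visit.** The earliest visit under 4.1 is 30 − 7 = day 23. The period in 7.1 ends at about day 30, so up to 30 − 23 = 7 days are still to run. The next contact in 1.3 is at 60 days. An event or DAPT interruption between days 23 and 30 would therefore not be looked for at any scheduled contact before the patient stops. The 60-day contact could find it, but only after cessation.

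**Final contact.** The earliest under 4.1 is about day 366, against about day 396 under 1.3: a shortfall of up to 30 days with no later scheduled contact. Section 8.1.4 records SAEs for 30 days after participation, so deaths and hospitalized MIs in that gap are captured if they are reported.

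**Upper bound on the endpoint effect.** The plan gives no figure for this. Inputs from the documents: reference rate 3.1% and n = 231 (9.2), final alpha 0.0492 (9.4.4). Assumptions: all 231 evaluable, constant hazard over a 365-day window, every last contact 30 days early, nothing captured afterwards, and early contacts counted as event-free.

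- Expected events: 231 × 0.031 = 7.16.
- Rate seen over 335 of 365 days: 1 − 0.969^(335/365) = 0.02849, or 2.85%.
- Events missed: 231 × (0.031 − 0.02849) = 0.58.
- Binomial test at p = 0.031: P(X ≤ 2) = 0.0247 and P(X ≤ 3) = 0.0707, so 2 is the largest significant count.
- Chance of 2 or fewer observed events when the true rate is 3.1% but reads as 2.85%: 0.0386, still below 0.0492.

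**A milder case.** If last contacts spread evenly over −30 to +30 days, the mean shortfall is 7.5 days. The rate reads as 1 − 0.969^(357.5/365) = 0.03037, about 0.14 events are missed, and P(X ≤ 2) = 0.0276.

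**The case against.** The strongest reply is that 4.1 is a narrative summary and 1.3 is the working schedule. Section 4.3 defines completion by the 1.3 schedule, and 6.1.1, which instructs the sites, repeats +7. This stands as evidence of intent and is why 1.3 should be the version kept. It does not remove the contrary windows from 4.1.

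Three stronger readings are tempting, and the documents do not support them.

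- **That the plan authorizes stopping at day 23.** Sections 4.2 and 5.1 and exclusion 4 in 5.2 keep DAPT at one month, and the bar in 7.1 still applies after an early visit. One withdrawal ground in 7.1 reads "The participant is unwilling or unable to discontinue DAPT within 7 days after 30-day post-procedure visit"; since 23 + 7 = 30, a day-23 visit is compatible with stopping on day 30. What remains is that the judgement is made early.
- **That a patient with a staged second PCI would be withdrawn under 7.1 for not stopping in time.** Withdrawal there is optional, and a patient kept on DAPT because exclusion 4 counts the month from the last PCI is neither unwilling nor unable to stop. The timing conflict also depends on counting visits from the index PCI, whereas 1.3 and 6.1.1 say only that they are post PCI. On that count a plus-only window would still allow a visit 30 − 7 = 23 days after a PCI staged on day 7, again with 7 days unjudged. That is a question of where the window is anchored, and ± does not cause it.
- **That events in the gap are lost.** The 60-day contact includes AE assessment, 8.1.4 requires asking about events since the last visit, and 8.1.6 requires SAE reports within 5 working days.

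Finally, the plus signs in 1.3 and 6.1.1 might be ± signs that did not survive conversion from PDF. The inconsistency would then vanish, but the day-23 problem would apply in all three sections.

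**Conclusion.** The point holds as a visit-timing and follow-up gap. As written, 4.1 permits an eligibility judgement up to 7 days before the period being judged has ended, with no scheduled contact before cessation. It also permits a last contact about 30 days before month 13.

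A reader might infer material bias in the primary endpoint; the figures do not support that. The 0.58 missed events of 7.16 is an upper bound under assumptions that set aside the SAE capture in 8.1.4, and the even-spread case gives 0.14. In both, the chance of a falsely significant result at 231 patients stays below 0.0492. The reason to act is the eligibility decision, which concerns withdrawal of antiplatelet treatment after stenting, together with the very low cost of the correction.

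**What to change.** 1. Change the windows in 4.1 to the plus-only windows of 1.3: +7, +14 and +30 days.
2. State that the 30-day window (+7 days) runs from the last PCI, including a staged one, so that eligibility assessment and P2Y12 cessation occur no earlier than day 30 after it. The anchor is needed: if the window stayed at days 30 to 37 after the index PCI, a patient staged on day 7 would have 7 + 30 = day 37 as the only permissible visit day. Anchored to the last PCI, the window becomes days 37 to 44 after the index.
3. State that the final contact occurs no earlier than month 13.

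The cost is protocol wording and a few rescheduled contacts. Sample size and analysis are unaffected.

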## 4.2 SCIENTIFIC RATIONALE FOR STUDY DESIGN

The proposed trial is designated as a prospective, single arm pilot investigation to assess safety endpoints following the application of DAPT in HRB patients undergoing iLab IVUS-guided PCI with the SYNERGY® Stent System.

The trial is designed as an observational, single arm, proof of concept study to determine if patients at high bleeding risk (HBR) who have IVUS guided SYNERGY™ Stent implantation can safely undergo DAPT cessation at 30 days post implantation. This is felt to be a prudent environment to appropriately and safely study this hypothesis and potentially enlighten future larger clinical trials.

## 4.3 END OF STUDY DEFINITION

A participant is considered to have completed the study if he or she has completed all phases of the study including the last visit or the last scheduled procedure shown in the Schedule of Activities (SoA), Section 1.3.

## 5 STUDY POPULATION

### 5.1 INCLUSION CRITERIA

In order to be eligible to participate in this study, an individual must meet all of the following criteria:

**General Inclusion criteria:**

1. Subject is considered at high risk for bleeding, defined as meeting one or more of the following criteria at the time of enrollment:
  - $\geq$  75 years of age and, in the opinion of the investigator, the risk of bleeding associated with  $>1$  months of DAPT outweighs the benefit,
  - Need for chronic or lifelong anticoagulation therapy

- History of major bleeding (severe/life threatening or moderate bleeding based on the GUSTO classification) within 12 months of the index procedure,
  - History of stroke (ischemic or hemorrhagic),
  - Renal insufficiency (creatinine  $\geq 2.0$  mg/dL) or failure (dialysis dependent),
  - Platelet count  $\geq 20,000/\mu\text{L}$  to  $\leq 100,000/\mu\text{L}$
  - In the opinion of investigator, patient is at significant risk of falling
  - Patient abuses drugs or alcohol
  - Hemoglobin  $\leq 11.0$
2. Subject must be 18 years of age
  3. Subject must be able to take study required dual antiplatelet therapy (1 month of P2Y12 inhibitor and aspirin, 13 months of antiplatelet monotherapy)
  4. Subject is willing to comply with all protocol requirements, including agreement to stop taking P2Y12 inhibitor at the 1-month milestone if eligible per protocol
  5. Subject (or legal guardian) understands the trial requirements and the treatment procedures and provides written informed consent before any trial-specific procedures are performed

#### **Angiographic Inclusion Criteria**

1. Subject must have had implantation of at least one SYNERGY™ Stent and the use of Boston Scientific IVUS for guided stent implantation
2. All implanted stents must be post dilated and must meet the following IVUS success criteria:
  - a) Treated lesions in which the stent cross sectional area exceeds the distal reference cross sectional area
  - b) The stent cross sectional area is less than the distal reference cross sectional area (if not additional post-dilatation must be performed, followed by repeat IVUS).
  - c) Above IVUS success criteria must be met after the 2nd post dilatation

Note: If IVUS success criteria is not met after the 2nd post dilatation then the patient is excluded

3. Stent procedure performed by an approved investigator
4. Vessel diameter  $\geq 2.25$  mm and  $\leq 4.0$  mm and lesion length  $\leq 34$  mm
5. Pre-dilatation is up to the discretion of the investigator

## **5.2 EXCLUSION CRITERIA**

An individual who meets any of the following criteria will be excluded from participation in this study:

#### **General Exclusion criteria:**

1. Subject with an indication for the index procedure of acute ST elevation MI (STEMI)
2. Subject with an indication for the index procedure of Non ST elevation MI (NSTEMI), based on the 3rd Universal MI definition
3. Subject with treatment with another coronary stent, other than SYNERGY, during the index procedure
4. Subject with a planned staged procedure  $> 7$  days following the index procedure. (Note: Planned staged procedures are allowed if performed within 7 days of the index procedure and only when

- SYNERGY™ stents are used for both the index and staged procedures). Discontinuation of DAPT should occur 1 month after the last PCI procedure is completed
5. A staged procedure cannot be in a 3rd epicardial vessel if 2 epicardial vessels were treated during the index procedure
  6. Subject has a known allergy to:
    - a. Contrast (that cannot be adequately pre-medicated),
    - b. SYNERGY™ Stent system (e.g., everolimus, structurally related compounds, polymer or individual components) or
    - c. Protocol-required concomitant medications ( all P2Y12 inhibitors and aspirin)
  7. Subject previously treated at any time with intravascular brachytherapy
  8. Subject has an active peptic ulcer or active gastrointestinal (GI) bleeding
  9. Subject is participating in an investigational drug or device clinical trial that has not reached its primary endpoint (Note: registry, observational, data collection studies are not exclusionary)
  10. Subject intends to participate in an investigational drug or device clinical trial within 12 months following the index procedure (Note: registry, observational, data collection studies are not exclusionary)
  11. Subject is judged inappropriate for discontinuation from P2Y12 inhibitor use at 1 month, due to another condition requiring chronic P2Y12 inhibitor use
    - a. If at the 30 day visit the patient has had a peri-procedural NSTEMI with an enzyme elevation >5% of the upper 99th percentile of either CK-MB or Troponin, the subject should not be taken off DAPT.
  12. Subject with planned surgery or procedure necessitating discontinuation of P2Y12 inhibitor within (≤)1 month following index procedure
  13. Subject is a woman who is pregnant or nursing
  14. Subject with a current medical condition with a life expectancy of less than 12 months
  15. Subject with implantation of a drug-eluting stent other than SYNERGY™ Stents within 11 months prior to index procedure
  16. Have been previously consented for this trial and screen failed
  17. Any other clinically significant comorbidities, which in the judgment of the Investigator, could compromise compliance with the protocol, interfere with interpretation of the study results, or predispose the patient to safety risks.

### **Angiographic Exclusion Criteria**

1. Target lesion(s) is located within a saphenous vein graft or an arterial graft
2. TIMI flow 0 (total occlusion)
3. Target lesion(s) is located in the left main
4. Potential Target lesion(s) that involve a complex bifurcation (i.e. bifurcation lesion requiring treatment with more than one stent)
5. Thrombus, or possible thrombus, present in the target vessel (by visual estimate)
6. Patients requiring a treatment of more than two native epicardial vessels.
7. More than three lesions in two epicardial vessels unless they can be covered by one stent.
8. Target lesion(s) with in- stent restenosis

9. Treatment of non-target lesions or lesions not treated with a SYNERGY™ stent
10. Subject who did not receive Boston Scientific IVUS guided stent implantation and assessment
11. Any target lesion that has **not** been post dilated and has **not** received post dilatation IVUS
12. Patients who do not meet the following IVUS success criteria:
  - Target lesion(s) in which the stent cross sectional area is less than the distal reference cross sectional area and additional post-dilatation is not performed, followed by repeat IVUS.  
\*\* Note: If the IVUS success criteria is not met after the 2nd post dilatation the patient is excluded

### 5.3 SCREEN FAILURES

Screen failures are defined as participants who consent to participate in the clinical trial but are not subsequently entered in the study. Screen failure information will be reported to meet the Consolidated Standards of Reporting Trials (CONSORT) publishing requirements and to respond to queries from regulatory authorities. This will include demographic, screen failure details, eligibility criteria, and any serious adverse events (SAE).

Individuals who do not meet the criteria for participation in this trial (screen failure) may not be rescreened.

## 6 STUDY INTERVENTION

### 6.1 STUDY INTERVENTION(S) ADMINISTRATION

#### 6.1.1 STUDY INTERVENTION DESCRIPTION

Coordinators will be trained by the Coordinating Center at HonorHealth Research Institute. Participants will be screened for Eligibility, and Informed Consent will be obtained. Detailed procedural data will be obtained by the Study Coordinator and Site Principal Investigator, and participants will undergo a Baseline Interview. These data will be entered into the electronic data capture system with stringent protections and quality controls.

The SYNERGY™ Stent System is already FDA-approved for improving luminal diameter in patients with atherosclerotic lesions in native coronary arteries  $\geq 2.25$  mm to  $\leq 4.0$  mm in diameter in lesions  $\leq 34$  mm in length. This includes those with diabetes mellitus, with symptomatic heart disease, stable angina, unstable angina, non-ST elevation MI or documented silent ischemia.

#### Pre Procedure Tests and Procedures (Up to 7 days prior to the procedure)

- Standard Laboratory Values: Basic Metabolic Panel, CBC w/ differential and platelets
- Cardiac Enzymes: Total CPK/CK-MB or Troponin I

- PT-INR: If not part of standard of care draw only if patient is taking warfarin, has liver disease or severe anemia
- 12 Lead ECG

### Procedure

Study subjects will undergo PCI using the SYNERGY™ Stent System with iLab IVUS-guidance following the SYNERGY™IFU (instructions for use). If bailout stenting is required, a SYNERGY™ stent should be used if a stent of appropriate length and diameter is available. If not available, an approved coronary stent should be used.

#### Per the SYNERGY IFU:

- Target lesion vessel diameter  $\geq 2.25\text{mm}$  and  $\leq 4.0\text{mm}$
- Target lesion length  $\leq 34\text{mm}$
- No ostial lesions (within 5 mm of RCA ostium, 3 mm of left main)
- No complex bifurcations
- No TIMI flow  $\leq 1$  distal to lesion
- No In-stent restenosis
- No CTOs
- No Overlapping stents

